6.2 Missing Data

Data that are reported as missing will be treated as missing in all data summaries. Imputation rules for partially recorded dates, in case that the complete dates are required to carry out an analysis, will be provided in the Statistical Programming Plan (SPP). In descriptive summaries for safety, observations that are spurious (extreme relative to the majority of the data) will not be altered or removed from the summary.

6.3 Patient Disposition and Baseline Characteristics

6.3.1 Patient Disposition

For patient disposition, the number and percentage of patients who reach various study milestones are summarized: All screened patients are broken down by screen failures (with reasons if collected) and enrolled. Then the category of enrolled is broken down by never treated (with reasons if collected) and treated. The category of treated will further be broken down by treatment ongoing and treatment discontinuation (with reasons for discontinuation, which also include protocol-defined treatment completion, if any). The end of study status for

all enrolled patients will also be included. Duration of study, defined as time from the date of first dose of MGD007 to the date of withdraw of consent, lost to follow up, death, or the last contact date, will be summarized.

6.3.2 Patient Demographics and Baseline Characteristics

Patient demographics, baseline disease characteristics (e.g., KRAS mutation and MMR status), disease history, medical history, prior cancer therapy, and other collected baseline data will be summarized using descriptive statistics.

6.4 Study Drug Exposures and Concomitant Medications

Study drug exposure and concomitant medications will be summarized by descriptive statistics.

The summary of study drug exposure will include descriptive statistics as well as frequency counts for the number of doses or cycles received, the total dose actually administered as well as the total dose intended, and the dose intensity which is calculated as percentage of total dose actually administered divided by total dose intended during whole treatment period. Dose intensity by cycle may be summarized. Duration of study treatment exposure will also be summarized.

The summary of concomitant medications will include the number and percentage of patients who receive any concomitant medications as well as each concomitant medication by drug class.

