#### **4.4 Guidelines for Dose Modification**

No dose modifications will be allowed with exception of 1) reduction of infusion rate during re-challenge for patients experiencing an infusion reaction ([Section 7.2](#)) or 2) reduction of dose in patients receiving MGD007 or MGA012 at a dose that is subsequently determined to exceed the MTD ([Section 4.1.1](#)).

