##### **4.4.1 Dose Delays in Escalation and Expansion Cohorts**

Patients who experience toxicity that is potentially dose-limiting should have study drug held pending assessment, management, and resolution of the toxicity. For patients in whom the toxicity is assessed to be unrelated to study drug or for whom the toxicity does not meet the

criteria for DLT, therapy may be re-instituted at the same dose and schedule that was administered prior to the event, presuming the toxicity has resolved as per guidelines outlined in [Section 7](#). Dose interruptions of up to 28 days are allowed. Reinstitution of therapy shall be conducted as follows:

- The procedures at the originally scheduled missed visit should be performed as soon as possible with treatment reinstated as if no delay had occurred, picking up at the day where the interruption occurred, and patients should receive the planned dose and have assessments performed as outlined in the Time and Events Schedule ([Appendix 1](#)).

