## 5.4 Rules for Study Treatment Discontinuation

Patients who tolerate treatment may continue to receive treatment with the study drug(s) as specified in the protocol until any one of the following conditions are met:

- Patient meets any criteria for immune-related disease progression (irPD)
- Withdrawal of patient due to an AE or SAE
- Withdrawal of patient consent
- Completion of protocol-defined therapy
- Investigator discretion
- Pregnancy
- Occurrence of drug-related DLT
- Dose delay > 28 days due to drug-related AE
- Repeated administration of prohibited concomitant medications
- The Sponsor, Investigator, or Regulatory Agency terminates the study
- Death

For individual patients who meet these criteria, but who are otherwise considered to be experiencing compelling clinical benefit in the judgment of the Investigator, consideration may be given to continue treatment with the MGD007 and MGA012 combination, for up to maximum of total of 12 cycles, on a case-by-case basis, in consultation with the Sponsor.

For patients who experience drug-related DLTs that occurs prior to the initiation of MGA012, or for selected immune-related adverse events clearly related to the mechanism of action of MGA012, continued treatment of patients with either MGA012 or MGD007 monotherapy, respectively, may be considered selectively on a case-by-case basis, in consultation with the Sponsor.

If the Investigator decides that the patient should be withdrawn from the study or from dosing for any reason other than disease progression, the site must enter the information in the eCRFs within 24 hours ([Section 12.2.2](#)).

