## 7.5.1 Hepatic Toxicity

### 7.5.1.1 Elevations in Transaminases

Treatment management algorithm for patients experiencing hepatic toxicity are as follows:

- Grade 1 elevations - No specific therapy required.
- Grade 2 elevations - For elevations in transaminases 3 to  $5 \times$  ULN, rule out viral and other etiologies, and consider immediate oral steroids such as prednisone 60 mg/day divided twice daily, and hold MGD007 and MGA012.
  - If improvement to  $\leq$  Grade 1 does not occur within 48 hours consider IV steroids such as methylprednisolone at 2 mg/kg/day divided twice daily or oral steroids such as prednisone 60 to 120 mg per day, divided twice daily.
  - Resume MGD007 and MGA012 at the next scheduled dose if no more than 2 doses of the combination were missed.
  - If improvement to  $\leq$  Grade 1 does not occur within 14 days, discontinue MGD007 and MGA012.
- Grade 3 elevations - Hold MGD007 and MGA012.
  - For elevations in transaminases  $> 8 \times$  ULN, permanently discontinue MGD007 and MGA012.
    - Begin immediate IV steroids, and
    - If no response to corticosteroid therapy within 3 to 5 days is observed, consider adding immune suppression therapy with mycophenolate.
    - Monitor liver function tests at least twice weekly (or more frequently as clinically appropriate in the judgment of the Investigator) until transaminases have returned to Grade 1 or baseline.
  - For elevations in transaminases  $> 5$  but  $\leq 8 \times$  ULN:

- Begin immediate IV steroids; suggest methylprednisolone at a dosage of 2 mg/kg/day divided twice daily.
- Consider additional immune suppression as above for patients who do not respond to corticosteroid therapy within 3 to 5 days.
- Monitor liver function tests at least twice weekly (or more frequently as clinically appropriate in the judgment of the Investigator) until transaminases have returned to Grade 1 or baseline.
- If the elevation does not improve to Grade 2 within 7 days and to Grade 1 within 14 days, discontinue MGD007 and MGA012.
- Resume MGD007 and MGA012 administration if following conditions are met:
  - Laboratory elevations downgrade to  $\leq$  Grade 2 within 7 days and improve to  $\leq$  Grade 1 or baseline within 14 days.
  - Steroids have been tapered to  $\leq$  10 mg per day of prednisone or equivalent.
  - On resuming MGD007 and MGA012, AST, ALT, and total and direct bilirubin laboratory test values will be evaluated at least once per week for 3 consecutive weeks.

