## 14.4 Study Drug Exposures and Concomitant Medications

Study drug exposures and concomitant medications will be summarized by descriptive statistics. The summary of study drug exposure will include descriptive statistics as well as frequency counts for the number of doses or cycles received, the total dose actually administered as well as the total dose intended, and the dose intensity which is calculated as percentage of total dose actually administered divided by total dose intended during whole treatment period. Dose intensity by cycle will be summarized.

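### Dose intensity has no time term and leaves the intended dose undefined, so the same toxicity hold can read 100% or well below it, depending on how held doses are counted

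*SAP*

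**What the plan says.** SAP 6.4 summarises doses or cycles received and the amounts given and planned. It also defines "the dose intensity which is calculated as percentage of total dose actually administered divided by total dose intended during whole treatment period". Protocol 14.4 uses the same definition and also tabulates "the total dose actually administered as well as the total dose intended". Neither defines the intended dose. By-cycle dose intensity is optional in the SAP and committed to in the protocol. The SAP adds a summary of exposure duration, and SAP 6.7.1 tabulates adverse events leading to interruption or withdrawal of an individual drug.

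Protocol 4.4.1 says "Dose interruptions of up to 28 days are allowed" and has "treatment reinstated as if no delay had occurred, picking up at the day where the interruption occurred", at the planned dose. Protocol 5.4 lists "Dose delay > 28 days due to drug-related AE" among the reasons to stop treatment. Section 4.4 opens "No dose modifications will be allowed with exception of" and then names two exceptions: a slower infusion rate on re-challenge, and "reduction of dose in patients receiving MGD007 or MGA012 at a dose that is subsequently determined to exceed the MTD".

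Section 7.5 is worded differently. For Grade 2 transaminase elevations, 7.5.1.1 says "Resume MGD007 and MGA012 at the next scheduled dose if no more than 2 doses of the combination were missed". The pneumonitis, dermatologic and nephritis guidance (7.5.3 to 7.5.5) likewise restarts treatment at the next scheduled dose.

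**The concern.** With dose reduction confined to doses above the MTD, holding drug is a main route by which toxicity lowers exposure. Holds are foreseeable. Protocol 2.3.4 reports Grade 3 or greater drug-related diarrhea in 23 of 75 patients (31%) on MGD007 alone, across all doses and schedules, and Section 7.3 holds both drugs for Grade 3 diarrhea.

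A ratio of doses given to doses intended, applied to a schedule that slides with each delay, does not register a hold. The sections also differ on whether a held dose slides or is lost, so two patients with the same hold could receive different values, and two programmers could compute different values for one patient. Tolerability is part of the primary escalation objective and a secondary expansion objective, and this is the summary a reader would consult to see how much of the planned treatment was delivered.

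**Working it through.** The documents state no dose-intensity figure, so there is none to reproduce.

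**Inputs.**
- MGD007 is weekly in 8-week cycles (Protocol 4.1): 8 doses per 56 days.
- MGA012 is every 2 weeks from Cycle 1 Day 15: 3 doses in Cycle 1 (Days 15, 29, 43).
- The maximum single interruption is 28 days (4.4.1). No limit on the number of interruptions is stated.
- All infusions are assumed complete and at the assigned dose.

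Let *c* be the number of cycles and *h* the total days held.

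**Count on the shifted schedule (4.4.1).** Ratio = 8c / 8c = 100% for any *h*.

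**Dose per unit time on the same course.** (8c / (56c + h)) / (8c / 56c) = 56c / (56c + h).

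| Cycles | 7 days held | 14 days held | 28 days held |
|---|---|---|---|
| 1 | 56/63 = 88.9% | 56/70 = 80.0% | 56/84 = 66.7% |
| 2 | 112/119 = 94.1% | 112/126 = 88.9% | 112/140 = 80.0% |
| 6 | 336/343 = 98.0% | 336/350 = 96.0% | 336/364 = 92.3% |

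A single hold is diluted by longer treatment. Repeated holds offset this: two 28-day holds over two cycles give 112/168 = 66.7%.

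**Count over calendar time.** If the intended dose means one MGD007 dose per week elapsed, a 28-day hold in one cycle gives 84/7 = 12 intended doses and 8/12 = 66.7%. The SAP ratio then does show the delay.

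**Held doses skipped (Section 7.5 wording).** Two of 8 MGD007 doses skipped gives 6/8 = 75.0%. One of 3 Cycle 1 MGA012 doses skipped gives 2/3 = 66.7%.

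**The same hold under each reading.** A 14-day hold of MGD007 in one cycle covers two weekly doses. The SAP ratio is:
- 8/8 = 100% if the doses are postponed and intended doses follow the shifted schedule;
- 8/10 = 80.0% if they are postponed and intended doses are counted by calendar week (70/7 = 10);
- 6/8 = 75.0% if they are skipped.

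**Do the other summaries fill the gap?** By-cycle dose intensity on the shifted schedule does not, because a delayed cycle still holds 8 of 8 doses. Exposure duration lengthens with a hold but does not separate time held from time treated. The interruption table counts patients with such events, not days held.

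**The case against.** The strongest reply is that the SAP does not fix the denominator. The words could be read as calendar time, in which case the ratio detects delay, and programming detail is left to a separate statistical programming plan that is not among the documents. Protocol 4.4.1 also makes resumption conditional on resolution under Section 7, where several entries imply skipped doses, and those lower the ratio. In addition, number of doses, total doses and treatment duration are all tabulated, so a careful reader could infer a substantial delay.

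Most of this stands, and it limits the point. A reader might infer that dose intensity will sit near 100% however long patients are held. The documents do not support that. Each interruption is limited to 28 days, and a longer drug-related delay is a listed reason to stop, although 5.4 allows case-by-case continuation. Many of the toxicity entries in Section 7 make resumption depend on recovery within 14 days. Skipped doses, stopped infusions and above-MTD reductions all lower the numerator. The 66.7% figure is also an extreme: a maximum-length hold in a patient with a single cycle.

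A reader might also infer that the table would cause an undeliverable dose to be selected. Nothing in Protocol 4.3 supports that. Escalation rests on DLTs and safety review, and the expansion dose on PK, PD, biomarker, safety and response data, with no dose-intensity threshold.

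The reply does not remove the ambiguity. That the ratio might be read one way or another is itself the reason to define it, and no planned summary in the SAP reports days held.

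**Conclusion.** The point holds in limited form. Dose intensity as written has no time term and an undefined denominator. On the shifted-schedule count it cannot show delay: one 28-day hold reads 100%, when delivery per unit time is 66.7% of plan over one cycle, 80.0% over two and 92.3% over six. On the calendar or skipped-dose readings it does fall, so the value depends on a choice the plan has not made.

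These figures assume full infusions at the assigned dose and one hold that is later resumed. How often holds will occur under the combination is unknown, so the effect on cohort summaries cannot be sized. The consequence is confined to a descriptive exposure table that informs the tolerability objectives. It is worth correcting before analysis but does not affect the validity of the design.

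**What to change.** In SAP 6.4 and Protocol 14.4:

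1. Define the total dose intended. State whether it follows the shifted visit schedule or calendar time, and how it is counted when a patient continues on one drug alone (Protocol 5.4 and Appendix 1 allow for this).
2. For each drug, report relative dose intensity per unit time: cumulative dose divided by actual weeks on that drug, as a percentage of the planned weekly rate. Actual weeks can run from that drug's first dose to its last dose plus one planned interval (7 days for MGD007, 14 days for MGA012). Report it overall and by cycle, and align the SAP and protocol on whether by-cycle reporting is optional.
3. Report the number of dose delays and total days delayed for each drug. Include a final hold that is never resumed, which the measure in item 2 would miss.

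Protocol 4.4.1 and Section 7.5 must be reconciled on whether a held dose is delayed or skipped. Which rule applies is a clinical decision for the sponsor; the analysis only needs one to be stated.

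The cost is SAP wording, a short protocol clarification and some programming. Actual infusion dates and times already go on the eCRF (Protocol 9.8.2), so no new data are needed. The reported figure may look less favourable than the plain ratio.

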6.5 Protocol Deviations

Critical protocol deviations will be identified prior to database lock for final analysis and will be listed and summarized.

6.6 Efficacy Endpoint Analyses

6.6.1 Analyses of Response Endpoints

Number and percent of patients with their best overall response will be summarized. The objective response rate (ORR) per RECIST v1.1 is estimated as the proportion of patients in response evaluable population who achieve BOR of CR or PR. Disease control rate is calculated as the proportion of patients who achieve a CR, PR, or SD. Progression-free survival rate at 16 weeks will be calculated by Kaplan-Meier method described in [Section 6.6.2.1](#), based on response evaluable population and safety population, respectively. The 2-sided 95% exact binomial CI of the response rates will be calculated. The response rates per irRECIST will be estimated similarly. Subgroup analyses of these response rates by KRAS gene type (wild and mutant) and by MMR status (MSS and MSI-H) will be performed.

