## 14.2 Analysis Populations

The study analyses will be performed on the following populations:

- **Safety Population:** All patients who received at least one dose of any study drug. This population will be used for analyses of safety, PD, and immunogenicity. It will also be used for summary of baseline data and analyses of PFS and OS.
- **Response Evaluable Population:** All patients who received at least one dose of any study drug, had baseline measurable disease, and had at least one post-baseline radiographic tumor assessment or discontinued treatment due to clearly documented, clinically progressive disease or death. This population will be used for summary of tumor assessment data and analyses of response rates.

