3.2 Sample Size

The study plans to treat approximately 104 patients: up to 27 in each of two treatment cohorts in Dose Escalation Phase and approximately 25 in the Cohort Expansion Phase in each of the two treatment cohorts.

The sample size of up to 27 patients for each cohort in the Dose Escalation Phase is based on 3+3+3 design with planned 3 dose cohorts. Additional patients may be enrolled to replace non-evaluable patients or if the enrollment to a dose cohort is expanded (up to 15 patients) or intermediate dose levels are evaluated in Dose Escalation Phase.

The Cohort Expansion Phase plans to treat approximately 25 patients in relapsed/refractory metastatic colorectal carcinoma in each cohort, approximately 90% of them are MSS patients, e.g., 22 MSS and 3 MSI-H patients. At the end of the Cohort Expansion Phase, 15 paired tumor biopsies will be required in each cohort, if tumor lesions are accessible with acceptable clinical risk. If 15 paired biopsies have not been collected in the initial 25 patients, additional patients with paired tumor biopsies will be enrolled, to ensure that the 15 paired biopsies are obtained.

The sample size in the Cohort Expansion Phase is primarily based on providing preliminary estimation of objective response rate and disease control rate. [Table 1](#) provides the 2-sided 95% confidence interval (CI) for a number of potential responses among 25 patients in each cohort.

Table 1 **Response Rates and 95% Confidence Intervals**

Sample Size	Number of Responses	Response Rate (%)	95% Confidence Interval (%)
25	2	8	1.0, 26.0
25	3	12	2.5, 31.2
25	4	16	4.5, 36.1
25	5	20	6.8, 40.7
25	6	24	9.4, 45.1
25	7	28	12.1, 49.4

During the Cohort Expansion Phase, patients who withdraw before completing the first tumor assessment for a reason other than clinically confirmed progressive disease or death is considered unevaluable for response. In these cases, replacement patients may be enrolled in the same dose level.

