4 ANALYSIS POPULATIONS

4.1 Analysis Populations

The study analyses will be performed on the following populations:

- **Safety Population:** All patients who received at least one dose of any study drug. This population will be used for analyses of safety, PD, and immunogenicity. It will also be used for summary of baseline data and analyses of PFS and OS.
- **Response Evaluable Population:** All patients who received at least one dose of any study drug, had baseline measurable disease, and had at least one post-baseline radiographic tumor assessment or discontinued treatment due to clearly documented, clinically progressive disease or death. This population will be used for summary of tumor assessment data and analyses of response rates.

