6 STATISTICAL METHODOLOGY

6.1 General Considerations

This study is primarily observational and, thus, the majority of the statistical summaries will be descriptive. Safety and efficacy summaries will be provided for each dose level cohort during dose escalation and for all dose level cohorts combined, as well as for expansion cohorts where appropriate. Response rates will be calculated for the response evaluable population.

Unless otherwise specified, the following general considerations are applied in data analyses:

- The baseline value is defined as the latest value prior to the first dose of MGD007 treatment.
- Categorical data will be summarized by the number and percent of patients falling within each category.
- Continuous variables will be summarized by descriptive statistics, including mean, standard deviation, median, minimum, and maximum.
- Time-to-event endpoints will be summarized by the number and percent of the event, median time and corresponding 95% confidence interval (CI), and event free rate and corresponding 95% CI at the specified time points of interest.
- All data summaries and tabulations will be conducted using SAS® software Version 9.3 or higher.

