6.6.2 Analyses of Time to Event Endpoints

6.6.2.1 PFS and irPFS

The Kaplan-Meier method will be applied to estimate PFS curve, median PFS, and PFS rates at 4 (corresponding to 16 weeks), 6, and 12 months. The method of Brookmeyer and Crowley (1) will be used to construct 95% CI for median PFS. The 95% CIs for PFS rate at 4, 6, and 12 months will be calculated by normal approximation after log(-log) transformation.

For primary PFS analysis, the following table describes the censoring rules.

Table 2 Censoring Rules for Primary PFS Analysis

Situation	Date	Outcome
No baseline tumor assessments	First dose date	Censored
Death prior to first scheduled tumor assessment	Date of death	Progressed
No post-baseline tumor assessments in absence of death prior to first scheduled tumor assessment	First dose date	Censored
Documented progression	Date of progression	Progressed
Initiation of alternative anti-cancer treatments in absence of documented progression	Date of last tumor assessment prior to initiation of such treatment	Censored
Death or documented progression immediately after missing two or more consecutive scheduled tumor assessments	Date of last tumor assessment prior to missed assessments	Censored

PFS will be analyzed by MMR status and by KRAS gene type when sample size warrants. A sensitivity analyses for PFS may be performed to assess the robustness of above primary PFS analysis. For this sensitivity analysis, the censoring rules are the same as in **Table 2** except that the documented progression or death will be considered as an event, regardless of when it occurs during the study.

In addition, above analyses for PFS will also be repeated for irPFS.

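### ORR and DCR are planned only in the Response Evaluable Population; a supportive all-treated analysis should stand beside them, because the planned rates can equal or exceed the all-treated rates but never fall below them

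*SAP*

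**What the plan says.** Protocol 3.2.1 and SAP 2.2.1 name ORR, DCR and the 16-week PFS rate as the measures of the primary expansion objective.

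- **ORR.** SAP 6.6.1, like Protocol 14.6.1, says that ORR "is estimated as the proportion of patients in response evaluable population who achieve BOR of CR or PR".
- **DCR.** The sentence that defines DCR names no denominator. The general rules supply it. SAP 6.1 says "Response rates will be calculated for the response evaluable population". Protocol 14.2 says of the Response Evaluable Population "This population will be used for summary of tumor assessment data and analyses of response rates", and SAP 4.1 agrees.
- **Who is evaluable.** Besides a dose of study drug and measurable disease at baseline, the patient must have "had at least one post-baseline radiographic tumor assessment or discontinued treatment due to clearly documented, clinically progressive disease or death".
- **Who is not.** SAP 3.2 deals with expansion patients who withdraw ahead of their first scan. Anyone leaving at that stage "for a reason other than clinically confirmed progressive disease or death is considered unevaluable for response. In these cases, replacement patients may be enrolled"; the dose level stays as it was.
- **All treated patients.** Among efficacy analyses, SAP 4.1 gives the Safety Population only PFS and OS. The 16-week PFS rate, however, is estimated "based on response evaluable population and safety population, respectively" (SAP 6.6.1).

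**The concern.** The first scheduled scan is at Cycle 1 Day 56. A patient can stop before then for reasons that include an adverse event, a drug-related DLT or withdrawal of consent (Protocol 5.4). If no scan follows, the patient is absent from two primary measures and another patient may take the place.

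Some early stoppers may still be captured by the end-of-treatment scan or the 3-monthly response follow-up. Neither is guaranteed: Protocol 9.11 makes the visit optional, and footnote 3 of Appendix 1 collects follow-up response status only where it is available.

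The PFS analysis does not fill the gap. SAP Table 2 lists "No post-baseline tumor assessments in absence of death prior to first scheduled tumor assessment" as a situation censored at the first dose date, so these patients add nothing to the primary 16-week estimate even in the Safety Population. The alternative is optional, "A sensitivity analyses for PFS may be performed to assess the robustness of above primary PFS analysis", and adds only later deaths or documented progressions.

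At stake is how the headline activity rates are read: as the rate among patients who started treatment, or as the rate among those who reached an assessment.

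**Working it through.** **1. The plan's own figures.** SAP Table 1 (Protocol Table 13) gives two-sided 95% intervals for 2 to 7 responses in 25 patients. Exact binomial (Clopper-Pearson) limits reproduce all six rows, for example 2/25 = 8% (1.0-26.0), 5/25 = 20% (6.8-40.7) and 7/25 = 28% (12.1-49.4). The same method is used below. The SAP still describes 25 patients in each of two cohorts and Protocol Amendment 1 describes 25 in one; the arithmetic per cohort is the same.

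**2. Direction.** Let T be the number treated, E the number evaluable and r the number with the event.

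- SAP 5.1.1 requires CR and PR to be confirmed at least 4 weeks later, and SD to be observed at or after 8 weeks minus 3 days. A patient with no post-baseline scan can meet none of these.
- Measurable disease is an inclusion criterion (Protocol 5.1, number 6), so the missing scan is the practical route out of the denominator.
- All r events therefore lie among the E evaluable patients, and the ratio of planned to all-treated rate is (r/E)/(r/T) = T/E when r is at least 1. When r = 0, both rates are 0%. Since T is never smaller than E, the planned rate is never the lower one.

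**3. Size.** The documents state no exclusion rate. The range k = 1 to 5 is an assumption. The event counts (5 responses, 9 with disease control) are examples.

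*With replacement to 25 evaluable:* T/E = (25 + k)/25, from 26/25 = 1.04 to 30/25 = 1.20.

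| Measure | Planned (evaluable) | All treated, k = 1 | All treated, k = 5 |
|---|---|---|---|
| ORR | 5/25 = 20.0% (6.8-40.7) | 5/26 = 19.2% (6.6-39.4) | 5/30 = 16.7% (5.6-34.7) |
| DCR | 9/25 = 36.0% (18.0-57.5) | 9/26 = 34.6% (17.2-55.7) | 9/30 = 30.0% (14.7-49.4) |
| ORR, no response | 0/25 = 0% (0-13.7) | 0/26 = 0% (0-13.2) | 0/30 = 0% (0-11.6) |

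*Without replacement:* T/E = 25/(25 - k), from 25/24 = 1.04 to 25/20 = 1.25. An all-treated ORR of 5/25 = 20.0% would be reported as 5/24 = 20.8% (7.1-42.2) to 5/20 = 25.0% (8.7-49.1).

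In each of these cases the all-treated rate lies inside the exact 95% interval of the evaluable estimate.

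**4. Which measure is more likely to move.** This is illustration only. Protocol Table 2 reports 2 partial responses among 59 evaluable patients in CP-MGD007-01, one of them unconfirmed. The present SAP requires confirmation, so the matching count is 1. At 1/59, the chance of no response in 25 patients is (58/59)^25 = 0.65, in which case ORR does not move. For disease control that table gives 2 + 19 = 21 of 59, and (38/59)^25 is below 0.0001. The minimum for SD was 6 weeks there and is about 8 weeks here, so 21/59 is probably high. DCR remains the measure more likely to shift.

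**The case against.** The strongest reply is that this is a choice of estimand and not an error. Protocol and SAP agree on one prespecified population, and the rate among evaluable patients is estimated correctly. The definition already keeps unscanned patients who die early or have documented clinical progression, and counts them as failures. No decision depends on the result: SAP 6.1 calls the summaries mostly descriptive, SAP 3.2 sizes the expansion for preliminary estimation, and there is no test or threshold. The information is also recoverable. Best-response counts (SAP 6.6.1) and the number treated, with reasons for discontinuation (SAP 6.3.1), are both planned. Because an unscanned patient cannot be an event, events divided by treated gives the all-treated rate exactly, and its interval follows from the same two integers.

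All of this stands, and it limits the weight of the point. It does not remove it. ORR and DCR are primary measures and the stated basis of the expansion sample size, the difference can go only one way, and the plan already shows the third primary measure in both populations. Protocol 5.3 says that replaced escalation patients are considered in intention to treat, but it concerns the Dose Escalation Phase, and no such population is defined or assigned to ORR or DCR.

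A reader might also take the fall from 75 treated to 59 evaluable patients in CP-MGD007-01 (Protocol 2.3.4) as the exclusion rate to expect. The documents do not support that. It is an interim data cut, no reasons are given, and the evaluable definition under Protocol Table 2 does not list death, whereas patients who discontinue because of death stay evaluable here. Choosing particular cohorts from that study does not cure this.

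**Conclusion.** The point holds as a modest, one-directional effect on two primary measures. The planned ORR and DCR are higher than the all-treated rates by exactly treated/evaluable when at least one event is seen, and equal otherwise. Under the assumed 1 to 5 exclusions the factor is 1.04 to 1.20 with replacement and 1.04 to 1.25 without. The result rests on that assumed range and on exclusions arising from a missing scan.

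A reader might infer that the planned rates are invalid, that every unscanned patient is left out, or that a conclusion of the trial could be reversed. None of these follows. The planned rates are correct for the population that they name, early deaths and documented clinical progressions stay in the denominator, no threshold exists to be crossed, and the shifts shown lie within the intervals. The change is worth making because it is cheap and is best specified before results are known.

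**What to change.** Keep the planned analysis. Add to SAP 6.6.1 and Protocol 14.6.1 a supportive analysis of ORR and DCR in the Safety Population, with exact 95% CIs, by RECIST 1.1 and by irRECIST. Count patients with no post-baseline assessment as non-responders, and as not having disease control for DCR. Include patients who were replaced. Show the result beside the Response Evaluable one, as is already planned for the 16-week PFS rate, with the number of excluded patients and the reasons. Naming the denominator in the DCR sentence itself would also help.

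The cost is wording in two documents and one extra table, with no new data and no change to the sample size. The downside for the sponsor is that the added rates will be equal to or slightly less favourable than the planned ones.
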